## **Introduction**

### **1.1 Purpose of the Statistical Analysis Plan (SAP)**

This statistical analysis plan has been developed to (1) provide a structured time-frame for database completion and preparation of the final primary analysis report; (2) facilitate discussion of the key statistical analysis components amongst the study team; (3) provide agreement between the study team and statisticians regarding the statistical analyses to be performed; and (4) aid in setting priorities relating to the data cleaning and development of statistical analysis programs.

The statistical analysis plan contains details of all statistical analyses that will be completed for the final primary analysis report.

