## **2 Study Objectives (Protocol Version 2.0)**

The primary analysis report will include the primary objective and secondary objectives 1-4 (listed in sections 2.1 and 2.2 below). Secondary objectives 5-7 and the exploratory objectives (section 2.3) will be addressed in separate analysis plans.

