### **2.2 Secondary Objectives**

1. To compare safety and toxicity of INH *in utero* exposure and on infants on study
2. To compare TB incidence and all-cause mortality in HIV-infected women and their infants enrolled on study
3. To compare overall safety and hepatotoxicity, as well as evaluate risk factors for these outcomes, during pregnancy and immediate postpartum in women on immediate versus deferred INH therapy
4. To evaluate for INH resistance among *M.tb.* isolates from HIV-infected women and infants who develop TB while on study
5. To evaluate the intensive pharmacokinetics of INH and selected ARV drugs in a subset of HIV-infected pregnant and postpartum women receiving HAART
6. To evaluate and compare the performance characteristics of IGRA (TB ELISPOT and QGIT) with TST in HIV-infected women and their infants
7. To compare adherence in women initiating immediate versus deferred INH preventive therapy via self-report and pill counts

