### **3.2 Secondary Endpoints**

- ***In utero* exposure and infant endpoints:**
  - Fetal death
  - Small for gestational age
  - Premature birth (< 37 weeks gestation)
  - Low birth weight (< 2500 gm)
  - Congenital anomalies
  - Grade 3 or higher clinical or laboratory AEs
    - ◆ all AEs
    - ◆ possibly, probably, or definitely related to INH/Placebo for INH
  - HIV infection
  - Hospitalization
- **Any of the following endpoints:**
  - Maternal TB (probable or confirmed – see Appendix 100 for definitions)
  - Infant TB (probable or confirmed, as defined in Appendix 100, and congenital TB, as defined using the Cantwell criteria)
  - Death of infant
  - Death of mother
  - Combined endpoint of maternal TB or maternal death
  - Combined endpoint of infant TB or infant death
  - Combined endpoint of maternal TB, maternal death, infant TB, or infant death

NOTE: TB endpoints and infant cause of death will be reviewed by a Secondary Endpoint Review Committee (SERC), which consists of maternal and pediatric TB specialists who may be

members of the study team. Refer to the Endpoint Review Process document for details of the review process. Appendix 100 will be the basis for adjudication of the TB endpoint by the SERC and is available in the CRF Appendix Codes section of the Frontier Science IMPAACT Portal; the web link to portal can be found in the MOP. Cantwell criteria for Congenital TB are in the MOP and will be collected on the P1078 CRF.

Deaths of enrolled women will receive external review by the IERC for adjudication of study treatment attribution and will also be reviewed by the SERC. The SERC will consider if the cause of death (COD) is due to unrecognized active TB (expected to be rare), from a known cause other than active TB, or from an unknown cause.

- **Occurrence of each of the following safety outcomes in HIV-infected women: during pregnancy up to: (i) delivery (antenpartum) and (ii) 12 weeks postpartum**
  - Grade  $\geq$  3 AEs possibly, probably, or definitely related to INH/Placebo for INH or permanent discontinuation of INH/Placebo for INH due to an adverse event
  - Grade  $\geq$  3 AEs (all-cause)
  - Hepatotoxicity possibly, probably, or definitely related to INH/Placebo for INH
  - Hepatotoxicity (all-cause)

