#### 4.1.1 Sensitivity analyses of the primary objective

The following sensitivity analyses will be performed: (i) per-protocol, which will include and compare only participants who initiated and completed the regimen to which they were randomized according to the protocol (ie. completed study treatment or discontinued due to death or toxicity); and (ii) as-treated, which will compare participants according to the actual treatment received (ie. participants in the deferred arm who started INH in the antepartum period will be analyzed in the immediate arm).

Sensitivity analyses will be done to assess the impact of coding deaths of unknown cause and all deaths as events. Supplementary analyses will include estimation of the difference in primary endpoint rates between the two arms based on simple estimates of proportions stratified by gestational age, where endpoints will be assessed based on available data (i.e. if participant discontinued the study early and did not experience an endpoint up until that point, then assume no endpoint was reached). Un-weighted (i.e., ignoring stratification by gestational age) estimates for the difference in rates will also be reported.

Multivariable analyses to adjust for maternal characteristics such as treatment arm, age, duration on HAART, CD4 count, gestational age at study entry, IGRA positivity at study entry in all women, and other potential confounders such as HBsAg serology status at entry will be performed using Poisson regression modeling.

Finally, similar analyses will be performed on all Grade  $\geq 3$  AEs (regardless of INH/Placebo for INH attribution) as a way to check for bias in the primary endpoint analysis.

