#### 4.2 Analysis of Secondary Objectives

Maternal TB, maternal death, infant TB and infant death will be analyzed separately and as combined events. Efficacy of INH will be assessed primarily by comparing event rates between women in the immediate and deferred arms by 48 weeks postpartum.

A 95% confidence interval for the absolute difference in event rates will be computed using study entry gestational age-stratified Mantel-Haenszel estimates. Unweighted (i.e., ignoring stratification) estimates for the difference in rates will also be reported.

Strategies for censoring will vary depending on the efficacy outcome of interest. For analyses of maternal TB, any maternal death not caused by TB will not be considered an event and any maternal death of unknown cause will be considered an event. Similarly, for analyses of infant TB, any infant death not caused by TB will not be considered an event and any infant death of unknown cause will be considered an event. Sensitivity analysis to assess the effect of this strategy includes coding death due to unknown cause as a non-event.

This will be a modified intent-to-treat analysis, with participants analyzed according to randomized study arm, excluding those who were determined to have active TB at entry.

For final analyses, supplementary analyses will include estimation of differences in these individual/combined endpoint rates between the two arms based on simple estimates for proportions.

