## 5.10 *In Utero* Exposure and Infant Outcomes

Validation: The analysis programs in this section will be validated, but not double-programmed.

Note: Exact categorical tests (with mid-p adjustment for the case of Fisher's exact tests) will be employed to compare the difference in outcomes between arms.

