### 5.10.1 Summary of pregnancy outcomes

- Table with number (%) of pregnancies by outcome type (eg. live birth, stillbirth, spontaneous abortion, induced abortion, discordant birth outcomes) and number of fetuses (singleton, twins)

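### Pregnancy and infant safety outcomes under secondary objective 1 get only an exact test beside counts by arm, with no effect estimate or confidence interval, and small for gestational age has no table row

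*SAP*

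**What the plan says.** Section 1.1 claims completeness: "The statistical analysis plan contains details of all statistical analyses that will be completed for the final primary analysis report". Section 2 sets the scope: "The primary analysis report will include the primary objective and secondary objectives 1-4". Objective 1 in section 2.2 is comparative ("To compare safety and toxicity of INH" in utero and in infants). Section 3.2 lists its endpoints: fetal death, small for gestational age, premature birth, low birth weight, congenital anomalies, infant grade 3 or higher adverse events (all, and related to study drug), HIV infection and hospitalization.

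Section 5.10 gives one inferential method for these outcomes. Exact categorical tests, with a mid-p adjustment where the test is Fisher's, "will be employed to compare the difference in outcomes between arms". The outputs that follow are numbers and percentages, descriptive summaries and listings.

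Section 4.2, the methods text for secondary objectives, opens with "Maternal TB, maternal death, infant TB and infant death will be analyzed separately and as combined events" and attaches its 95% interval to those events. Infant death therefore has a planned estimate, in section 5.11, if event numbers warrant it.

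"Small for gestational age" stands as an endpoint in section 3.2, and the note heading section 5.10.3 says which births it is assessed on. Neither table below that note lists it.

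**The concern.** Objective 1 asks whether isoniazid in pregnancy harms the fetus or infant, and no margin is set for these outcomes. For such a question the useful result is the range of excess risk that the data have not excluded. A p-value above 0.05 can come from a result that rules out all but a small excess, or from one that leaves a large excess open, and the p-value does not tell the reader which.

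The SAP handles comparable outcomes more fully. Maternal hepatotoxicity gets mid-p tests and differences with 95% intervals (section 5.5), and maternal safety endpoints get stratified Mantel-Haenszel differences (section 5.9). Fetal and infant harm would thus be reported with less information than maternal harm. One named endpoint could also drop out of the report altogether.

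**Working it through.** **Textual check.** Between-arm methods planned for each group of outcomes:

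| Outcomes | Test | Difference between arms | Section |
|---|---|---|---|
| Primary and all-cause maternal safety | none listed | stratified Mantel-Haenszel | 4.1, 5.9 |
| Hepatotoxicity | Fisher mid-p | stratified Mantel-Haenszel, 95% CI | 5.5 |
| TB and death, mother and infant | none listed | stratified Mantel-Haenszel, 95% CI, as events warrant | 4.2, 5.11 |
| Pregnancy outcomes, infant adverse events, HIV, hospitalization | exact, mid-p | none | 5.10 |

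**Illustration.** The SAP gives no risk, power or precision figure for these outcomes, so there is no planned figure to reproduce. From section 1.2, 950 women randomized equally give 950/2 = 475 per arm. This is a target; 400 per arm is shown as a lower case. All event risks are assumptions.

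The mid-p value is two-sided: hypergeometric probabilities of all tables less probable than the observed one, plus half the probability of tables equally probable. Limits for the risk difference use Newcombe's method. The simpler Wald formula, d ± 1.96·√[p₁(1−p₁)/n + p₀(1−p₀)/n], gives nearly the same.

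Take 71/475 = 14.9% in the deferred arm. With 90/475 = 18.9% in the immediate arm, d = 4.0 points, the standard error is √(0.1895·0.8105/475 + 0.1495·0.8505/475) = 0.0243, and 1.96·0.0243 = 4.8 points. The interval is −0.8 to 8.8 points.

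| Immediate events | Difference (points) | Mid-p | Upper 95% limit (points) |
|---|---|---|---|
| 60 | −2.3 | 0.30 | 2.1 |
| 71 | 0.0 | 0.96 | 4.6 |
| 90 | 4.0 | 0.10 | 8.8 |

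All three would be reported as non-significant.

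**Range over assumed risks.** Immediate-arm events are raised one at a time while mid-p stays above 0.05. Each cell shows deferred v immediate events, then the excess and its upper 95% limit in points.

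| Deferred risk | 475 per arm | 400 per arm |
|---|---|---|
| 3% | 14 v 26: 2.5, 5.2 | 12 v 23: 2.8, 5.8 |
| 5% | 24 v 39: 3.2, 6.4 | 20 v 33: 3.3, 6.8 |
| 10% | 48 v 67: 4.0, 8.2 | 40 v 58: 4.5, 9.1 |
| 15% | 71 v 93: 4.6, 9.4 | 60 v 81: 5.3, 10.5 |
| 20% | 95 v 120: 5.3, 10.6 | 80 v 103: 5.8, 11.5 |
| 25% | 119 v 146: 5.7, 11.3 | 100 v 124: 6.0, 12.2 |

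**Effect of stratifying.** If the 90 v 71 result splits as 48 v 38 of 190 and 42 v 33 of 285 (assumed strata), the Greenland-Robins Mantel-Haenszel interval is −0.7 to 8.7. Stratifying hardly changes the width; its purpose is to match the randomization.

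**Sparse events.** Simulation with the same assumed strata (200,000 trials per setting) gives coverage of the Mantel-Haenszel interval of about 90% at risks of 0.5% v 0.2%, and 94.7 to 95.0% at 2% v 1%, 2% v 2% and 5% v 2%. At 0.2% in both arms, 15% of intervals have zero width. Rare outcomes therefore need a fallback.

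**Twins.** Section 5.10.1 tabulates "number of fetuses (singleton, twins". If a share t = 1 to 3% of pregnancies are twin, with within-pair correlation ρ = 0.3 to 1 (both assumed), the design effect 1 + 2tρ/(1+t) is 1.006 to 1.058, so half-widths grow by 0.3 to 2.9%. This is small, and per-set analysis removes it.

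**The case against.** The strongest reply is that nothing here is wrong. The test is valid, counts by arm will be published, and any reader can work out a crude difference and interval from them. The primary decision does not depend on section 5.10. The illustration also uses event risks that the SAP does not supply. All of this stands, and it limits the severity. What remains is that a reader cannot recover the stratified estimate from arm totals, nothing would be prespecified, and the SAP already treats an interval as worth planning beside the same test for hepatotoxicity.

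A second reply is that one simple method will not suit every outcome. That also stands. Infant adverse events and hospitalization accrue to week 48 from birth, and simple proportions count an infant lost early as event-free. Section 4.1.1 offers "simple estimates of proportions stratified by gestational age" only as a supplementary analysis, and sections 5.5, 5.9 and 5.11 label simple proportions as sensitivity. They should not become the main estimate for followed outcomes. Likewise, setting HIV-positive against all other infants would count indeterminate and unknown status as uninfected.

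A reader might infer that the exact test is the wrong test, that no infant outcome gets an estimate, or that the SAP would read non-significance as proof of safety. The document supports none of these: overall infant death is estimated in section 5.11, and no passage equates a non-significant test with safety.

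**Conclusion.** The point holds as a gap in reporting. For the objective 1 outcomes the SAP fixes a test without an estimate or interval, and small for gestational age is left out of both adverse-outcome tables although it is a named endpoint. The missing row is a separate omission and stands on its own. Because section 1.1 claims to hold all analyses for this report and section 5.10 itself chooses the method, the gap cannot be put down to detail left for the protocol.

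On size: at 475 per arm and assumed deferred-arm risks of 3 to 25%, a non-significant result can leave an upper limit of 5.2 to 11.3 points of excess; at 400 per arm, 5.8 to 12.2 points. These figures rest on assumed risks and on target enrolment. They show what the p-value conceals, not what this trial will find. Severity is minor to moderate.

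**What to change.** Keep the mid-p tests and add to section 5.10 the between-arm risk difference with a 95% interval, stratified by gestational age at entry:

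1. **Outcomes fixed at birth** (fetal death, small for gestational age, premature birth, low birth weight, congenital anomalies and the section 5.10.3 composites): Mantel-Haenszel risk difference per pregnancy, with the denominators set by the section 5.10.3 note.
2. **Infant grade 3 or higher adverse events (all-cause and related) and hospitalization:** follow the pattern of sections 5.9 and 5.11, with the stratified Mantel-Haenszel event-rate difference as the main estimate and simple proportions as sensitivity. Analyse per mother-infant set so that twins are not treated as independent.
3. **Infant HIV infection:** positive versus negative among infants with determinate status, with indeterminate and unknown counts reported by arm.
4. **Sparse events** (for example fewer than 5 in either arm): an exact unstratified interval, with the method named in advance.
5. **Section 5.10.3:** add a small-for-gestational-age row, and state whether it enters the composites for any adverse pregnancy outcome.

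Overall infant death stays with section 5.11. The cost is SAP wording, two columns in planned tables and one row. No new data are needed, and the stratified estimators are already planned elsewhere in the SAP.

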### 5.10.1 Summary of pregnancy outcomes

- Table with number (%) of pregnancies by outcome type (eg. live birth, stillbirth, spontaneous abortion, induced abortion, discordant birth outcomes) and number of fetuses (singleton, twins)

### 5.10.2 Infant baseline characteristics

- Gender: number (%) by category [EVW0292]
- Gestational age at birth (weeks): N, N missing, min, max, median (Q1-Q3); number (%) by category (<34, 34 -<37,  $\geq 37$ )
  - Note: The calculation of gestational age at birth will be based on three sources, prioritized as follows: newborn exam [PE5896], pregnancy outcome evaluation [EVW0292] and mother's gestational age at enrollment [OBW0006] plus number of weeks to delivery.
- Birth weight (grams): N, N missing, min, max, median (Q1-Q3); number (%) by category (<1500, 1500 -<2500,  $\geq 2500$ ) [PE5896]

- Apgar score at 1 minute: N, N missing, min, max, median (Q1-Q3); number (%) by category (0-3, 4-6, 7-10) [PE5896]

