## 5 Report Components

Notes:

- *Unless otherwise indicated, all outputs will be by treatment arm.*
- *Data presented on individual participants will be identified by Public ID.*
- *Validation requirements per CBAR SOPs:*
  - *All programs that generate permanent study-specific derived datasets that contribute to the generation of reports for final analyses that either contain or are supportive of the analyses of the primary or secondary objectives will be validated; all such programs will undergo code review and execution checks, and the primary safety outcome measures will have results verification (double programming)*
  - *All programs that conduct key analyses for primary or secondary objectives will be validated; all such programs will undergo code review and execution checks, and those programs that conduct the analyses for the primary objective (maternal safety) will have results verification (double programming). The following analyses are considered key: Study/Treatment Status, Study Discontinuation prior to Evaluation of Primary Outcome, Maternal Safety, Infant Safety, Maternal TB, Infant TB. The level of validation required for each of the key analyses is specified below in the respective subsections.*

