### **5.10.3 Summary of adverse pregnancy outcomes**

Note: The evaluations of small for gestational age, premature birth, low birth weight and congenital anomalies are based on live births. Multiple births with both live birth and stillbirth outcomes will be counted as pregnancies with stillbirths and other adverse pregnancy outcomes that may have been observed. Pregnancy outcome of induced abortion will be excluded from adverse pregnancy outcome summaries.

- Table with number (%) of pregnancies resulting in each of the following adverse pregnancy outcomes:
  - Fetal demise (stillbirth, spontaneous abortion)
  - Premature birth (<37 weeks gestation)
  - Low birth weight (<2,500 grams)
  - Congenital anomalies
  - Any adverse pregnancy outcome excluding congenital anomalies (defined as any of the above excluding congenital anomalies)
  - Any adverse pregnancy outcome (defined as any of the above)
- Table with number (%) of pregnancies resulting in each of the following severe adverse pregnancy outcomes:
  - Fetal demise (stillbirth, spontaneous abortion)
  - Premature birth (<34 weeks gestation)
  - Low birth weight (<1,500 grams)
  - Any severe adverse pregnancy outcome (defined as any of the above)

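### Birth weight and gestational age at birth are outcomes of in utero exposure, but the SAP lists them as infant baseline characteristics and compares the arms formally only through cut-offs

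*SAP*

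**What the plan says.** Women are randomized between 14 and 34 weeks of gestation, and Arm A starts isoniazid at entry (SAP section 1.2). Secondary objective 1 (section 2.2) concerns the safety of that exposure for the fetus and infant.

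- **Where the variables sit.** Section 5.10.2, Infant baseline characteristics, has "Birth weight (grams): N, N missing, min, max, median (Q1-Q3); number (%) by category" and "Gestational age at birth (weeks): N, N missing, min, max, median (Q1-Q3); number (%) by category". The categories are <1500, 1500 to <2500 and ≥2500 g, and <34, 34 to <37 and ≥37 weeks.
- **How arms are compared.** The note at the head of section 5.10 reads: "Exact categorical tests (with mid-p adjustment for the case of Fisher's exact tests) will be employed to compare the difference in outcomes between arms".
- **Which endpoints are defined.** Section 3.2 lists "Low birth weight (< 2500 gm" and "Premature birth (< 37 weeks gestation" as binary endpoints. Section 5.10.3 tabulates these for live births and adds severe cut-offs at 1,500 g and 34 weeks.
- **Display.** Section 5 says: "Unless otherwise indicated, all outputs will be by treatment arm". The medians and quartiles will therefore appear side by side by arm.

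Elsewhere the SAP does compare continuous safety measures between groups: peak ALT (section 5.5) and the peripheral neuropathy score (section 5.6) each get a mean, SD and Wilcoxon test.

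**The concern.** A baseline table describes participants before treatment, and readers tend to treat a difference in it as chance. Here the infant has been exposed in the womb, in most cases for weeks, before either variable is measured, so a difference could be a drug effect.

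The second issue is precision. Both variables are collected as numbers, but the planned tests see only the side of a cut on which each infant falls. A modest shift in fetal growth or length of gestation could leave the low-birth-weight and preterm proportions not significantly different. In a trial that asks whether immediate therapy is as safe as deferred therapy, that result is easily read as reassurance. A confidence interval in grams or weeks would show which shifts the data exclude, and none is planned.

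**Working it through.** **Inputs from the SAP.** Target of 950 women, equal allocation, so 475 per arm before losses (section 1.2). Cut-offs of 2500 g and 37 weeks (section 3.2). The SAP states no power, SD, low-birth-weight rate, preterm rate or expected shift for these variables, so there is no planned figure to reproduce.

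**Assumptions.** Two-sided 5% (the SAP states a 5% level only for the primary analysis); normal birth weight with SD 500 g; the same shift in every infant; share p of control infants below the cut.

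**1. Information kept by one cut, birth weight.** Relative to a comparison of means, efficiency = φ(z)² / [p(1 − p)], where z is the normal quantile of p and φ the normal density.

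- p = 10%: 0.1755² / 0.09 = 0.342, loss 66%
- p = 15%: 0.2332² / 0.1275 = 0.426, loss 57%
- p = 20%: 0.2800² / 0.16 = 0.490, loss 51%
- Wider range: p = 5%, loss 78%; p = 30%, loss 42%

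Mean birth weights of 2900 to 3100 g with SD 450 to 550 g put p at 9% to 23% and the loss at 48% to 68%. Using all three birth-weight categories with optimal scores barely helps: efficiency is 0.35 to 0.52 with 1% to 3% of infants below 1500 g and 10% to 20% below 2500 g.

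**2. The same loss as power, 475 per arm.** The standard error of a mean difference is 500 × √(2/475) = 32.4 g. For a 100 g deficit, 100/32.4 − 1.96 = 1.12, which gives 87% power. The 2500 g cut sees:

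- 10.0% v 14.0%: power 47%
- 15.0% v 20.1%: power 55%
- 20.0% v 26.1%: power 60%

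For a 75 g deficit, power is 64% on the continuous scale against 29%, 34% and 38%. With 430 per arm and 100 g it is about 83% against 43%, 51% and 56%. The 95% interval at 475 per arm would have a half-width of 1.96 × 32.4 = 64 g.

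**3. Does this hold beyond a uniform normal shift?** Simulation, 475 per arm, 4,000 runs, Wilcoxon test against a two-proportion z test (standing in for the mid-p exact test). Control birth weight was normal with mean 3000 g and SD 500 g. Control gestational age was left-skewed, with about 11% below 37 weeks.

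| Scenario | Wilcoxon | Cut-off |
|---|---|---|
| Birth weight, all infants 100 g lighter | 86% | 58% |
| Gestational age, all 0.25 week shorter | 82% | 17% |
| Gestational age, 8% of infants 4 weeks earlier | 51% | 86% |
| Birth weight, 8% of infants 1000 g lighter | 44% | 58% |

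The continuous form does better for a general shift, and the cut-off does better when harm falls on a small subgroup.

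**The case against.** The strongest reply is that nothing here is wrong. Section 3.2 defines the endpoints as binary, section 5.10.3 implements them, and the exact test suits them. Section 5.10.2 sits under a parent heading on in utero exposure and infant outcomes, birth is where infant follow-up starts, and the same variables return as outcomes in 5.10.3. No planned model adjusts for them. By-arm medians and quartiles would let a reader see a shift. Small for gestational age, also listed in section 3.2, bears on growth.

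Most of that stands. A reader might infer that the SAP contradicts itself or removes these variables from outcome status. It does neither, and the label alone changes no result.

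A reader might also take a loss of half to two-thirds as a property of the plan. It is not: the SAP supplies no rate or SD, the figure is for birth weight under an assumed uniform normal shift, and it cannot be applied to gestational age. Nor is the cut-off always the less sensitive form, as the subgroup scenarios show.

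What the reply does not answer is that medians side by side carry no estimate of the difference and no uncertainty. Small for gestational age is itself a cut-off.

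**Conclusion.** The point holds as a weakness in efficiency and labelling. Two outcomes measured after exposure are filed as baseline, and the arms are never formally compared on the scale on which these outcomes are measured.

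For birth weight, assuming normality and a uniform shift, one cut loses about 51% to 66% of the information when 20% to 10% of infants lie below it, and 42% to 78% over 30% to 5%. For gestational age the loss depends on the shape of a skewed distribution, and no single figure can be given. Because the better form depends on how harm is spread across infants, the plan gains from having both.

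**What to change.** - Keep the cut-off endpoints and their exact tests as they are.
- In section 5.10.3, add as a supplementary analysis the between-arm difference in birth weight and in gestational age at birth (mean difference or Hodges-Lehmann estimate) with a 95% confidence interval, among live births, stratified by entry gestational age and allowing for twins.
- Retitle section 5.10.2 as birth characteristics.

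The cost is SAP wording and two estimates from data already collected. There are two drawbacks. Two comparisons join a long secondary list, so they should be labelled supportive. Gestational age at birth also draws on three prioritized sources (section 5.10.2), so a difference in weeks carries some dating error and should be reported with that caveat.
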